3.2.2. Viral Shedding Status and Duration of Viral Shedding

Viral shedding status will be determined for each participant on each study day during the challenge period, classified as follows:

- **RT-PCR+** if a qualitative RT-PCR result from the Biofire or Luminex multiplex assay is reported to be positive for Influenza A or Influenza A H3, and/or if a quantitative RT-PCR is reported to have detectable H3N2 virus.
- **RT-PCR-** if the qualitative RT-PCR results for Influenza A and Influenza A H3 are negative and the quantitative RT-PCR result indicates undetectable quantities of virus.

Detectable virus for the quantitative RT-PCR assay will be defined as being any quantity above a lower limit of detection (LLOD) reported by the laboratory conducting the assay.

Duration of viral shedding will be defined as time from the initial positive NP swab until the day after the final positive NP swab, with positivity defined as above. Intermittent negative results will be ignored for this computation.

3.2.3. Infection Status

Infection status, independent of symptom status, will be defined at the participant level in two different ways:

- Participants are considered **Infected** if viral shedding is detected in NP swab(s) by qualitative and/or quantitative RT-PCR on at least two days beginning 24 hours after challenge until Study Day 8
- Participants are considered to be **Currently Infected** from their first through their last study days meeting the viral shedding definition above (and in [Section 3.2.2](#)), regardless of any intermittent negative results between those two study days.

Pre-infection and post-infection results will be determined based on the definition of Current Infection above. New-onset symptoms will be those with a maximum severity post-infection (starting on the day of first RT-PCR positivity) above that of baseline, for infected participants.

3.2.4. Peak and Total Viral Shedding

Viral copies/mL will be estimated as a mean across quantitative RT-PCR replicates. Some replicates may be dropped from the calculations if potential quality control issues are noted. Values below the lower limit of detection will first be imputed as LOD/2 prior to taking the mean of the replicates.

Peak viral shedding will be calculated as the maximum viral concentration (RNA copies/mL) recorded the duration of the inpatient study period for each individual.

Total viral shedding over the inpatient period will be summarized by the area under the curve (AUC), approximated via the linear trapezoidal method, where the trajectory of an individual's viral concentration is

partitioned into $n-1$ subareas until the last inpatient observation at time t_n . As the linear trapezoidal AUC method approximates the entire area by calculating the cumulative sum of the subareas, the formula that will be applied is:

$$AUC_i = \frac{1}{2} * \sum_{j=1}^{n-1} (t_{j+1} - t_j) * (C_{ij+1} + C_{ij})$$

where $(t_{j+1} - t_j)$ is the difference between the j th and $j+1$ th time points within the inpatient period, and C_{ij} and C_{ij+1} are the viral concentrations measured at the j th and $j+1$ th time points for the i th individual. Intermittent missing values are expected to be minimal, so no imputation is planned.

3.2.5. Symptom Scores

The cumulative Modified Jackson Score (MJS; see [Figure 4](#)) will be calculated as described in [Section 3.2.1](#).

The area under the MJS curve will be calculated for each participant from Day 2 through Day 8, for uninfected participants (see [Section 3.2.3](#)), or from the first RT-PCR+ day through the last, for infected participants; this calculation will be made as described above in [Section 3.2.4](#) for total viral shedding, except in this case scaled by the number of days over which symptoms are summed.

The FLU-PRO total severity score is defined as the mean score across all 32 items (see [Figure 5](#)), with component scores ranging from 0 to 4. Six domain scores are also computed as mean scores, representing symptom severity in each body system. Scores will be computed for each study day utilizing the maximum severity score per symptom, and cumulative FLU-PRO scores (for the total FLU-PRO score and component scores) will be computed as the sum of the daily scores over the relevant time period.

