	Minimum	XX	XX	XX	XX	XX	XX	XX	XX	XX	XX	XX	XX
	Median	XX	XX	XX	XX	XX	XX	XX	XX	XX	XX	XX	XX
	Maximum	XX	XX	XX	XX	XX	XX	XX	XX	XX	XX	XX	XX
Area Under the Modified Jackson Score Curve per Day (Days 2 through 8 for uninfected participants, or during infection for infected participants)	Mean (95% CI) ^b	x.x (x.x, x.x)	x.x (x.x, x.x)	x.x (x.x, x.x)	x.x (x.x, x.x)	x.x (x.x, x.x)	x.x (x.x, x.x)	x.x (x.x, x.x)	x.x (x.x, x.x)	x.x (x.x, x.x)	x.x (x.x, x.x)	x.x (x.x, x.x)	x.x (x.x, x.x)
	Minimum	XX	XX	XX	XX	XX	XX	XX	XX	XX	XX	XX	XX
	Median	XX	XX	XX	XX	XX	XX	XX	XX	XX	XX	XX	XX
	Maximum	XX	XX	XX	XX	XX	XX	XX	XX	XX	XX	XX	XX
Modified Jackson Score (Total), Study Day 15	Mean (95% CI) ^b	x.x (x.x, x.x)	x.x (x.x, x.x)	x.x (x.x, x.x)	x.x (x.x, x.x)	x.x (x.x, x.x)	x.x (x.x, x.x)	x.x (x.x, x.x)	x.x (x.x, x.x)	x.x (x.x, x.x)	x.x (x.x, x.x)	x.x (x.x, x.x)	x.x (x.x, x.x)
	Minimum	XX	XX	XX	XX	XX	XX	XX	XX	XX	XX	XX	XX
	Median	XX	XX	XX	XX	XX	XX	XX	XX	XX	XX	XX	XX
	Maximum	XX	XX	XX	XX	XX	XX	XX	XX	XX	XX	XX	XX
Cumulative FLU-PRO Score (Total)	Mean (95% CI)	x.x (x.x, x.x)	x.x (x.x, x.x)	x.x (x.x, x.x)	x.x (x.x, x.x)	x.x (x.x, x.x)	x.x (x.x, x.x)	x.x (x.x, x.x)	x.x (x.x, x.x)	x.x (x.x, x.x)	x.x (x.x, x.x)	x.x (x.x, x.x)	x.x (x.x, x.x)
	Minimum	XX	XX	XX	XX	XX	XX	XX	XX	XX	XX	XX	XX
	Median	XX	XX	XX	XX	XX	XX	XX	XX	XX	XX	XX	XX

Symptom Score	Statistic	10 ⁴ TCID ₅₀ Challenge Virus (N=X)			10 ⁵ TCID ₅₀ Challenge Virus (N=X)			10 ⁶ TCID ₅₀ Challenge Virus (N=X)			Sham Inoculum (N=X)		
		Infected ^a	Uninfected	All Participants in Dose Group	Infected ^a	Uninfected	All Participants in Dose Group	Infected ^a	Uninfected	All Participants in Dose Group	Infected ^a	Uninfected	All Participants in Dose Group
	Maximum	XX	XX	XX	XX	XX	XX	XX	XX	XX	XX	XX	XX
Cumulative FLU-PRO (Nose)	Mean (95% CI)	x.x (x.x, x.x)	x.x (x.x, x.x)	x.x (x.x, x.x)	x.x (x.x, x.x)	x.x (x.x, x.x)	x.x (x.x, x.x)	x.x (x.x, x.x)	x.x (x.x, x.x)	x.x (x.x, x.x)	x.x (x.x, x.x)	x.x (x.x, x.x)	x.x (x.x, x.x)
	Minimum	XX	XX	XX	XX	XX	XX	XX	XX	XX	XX	XX	XX
	Median	XX	XX	XX	XX	XX	XX	XX	XX	XX	XX	XX	XX
	Maximum	XX	XX	XX	XX	XX	XX	XX	XX	XX	XX	XX	XX
Cumulative FLU-PRO (Throat)	Mean (95% CI)	x.x (x.x, x.x)	x.x (x.x, x.x)	x.x (x.x, x.x)	x.x (x.x, x.x)	x.x (x.x, x.x)	x.x (x.x, x.x)	x.x (x.x, x.x)	x.x (x.x, x.x)	x.x (x.x, x.x)	x.x (x.x, x.x)	x.x (x.x, x.x)	x.x (x.x, x.x)
	Minimum	XX	XX	XX	XX	XX	XX	XX	XX	XX	XX	XX	XX
	Median	XX	XX	XX	XX	XX	XX	XX	XX	XX	XX	XX	XX
	Maximum	XX	XX	XX	XX	XX	XX	XX	XX	XX	XX	XX	XX

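### The divisor for the per-day area under the Modified Jackson Score curve, as worded, shrinks scores by an amount that depends on window length and so differs between infected and uninfected participants in one exploratory row of Table 43

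*SAP*

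**What the plan says.** SAP 3.2.4 defines the area for viral shedding by the linear trapezoidal rule. The trajectory is "partitioned into $n-1$ subareas until the last inpatient observation at time t_n", and each subarea is weighted by the time between its two observations.

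SAP 3.2.5 reuses that calculation for the MJS with two changes.

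- **Window.** "The area under the MJS curve will be calculated for each participant from Day 2 through Day 8, for uninfected participants", "or from the first RT-PCR+ day through the last, for infected participants".
- **Scaling.** The calculation is the same "except in this case scaled by the number of days over which symptoms are summed". No formula for this divisor is given.

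The infected window varies between participants. SAP 3.2.3 calls a participant infected when shedding is detected "on at least two days beginning 24 hours after challenge until Study Day 8", and current infection runs from the first to the last such day "regardless of any intermittent negative results between those two study days".

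Table 43 reports the result in a row labelled "Area Under the Modified Jackson Score Curve per Day (Days 2 through 8 for uninfected participants, or during infection for infected participants"). Each dose group has three columns: infected, uninfected and all participants.

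**The concern.** The purpose of scaling per day is to make windows of different length comparable. Dividing by the number of days with scores is right for a sum of daily scores. Here it is applied to an area, which has one interval fewer than it has days, so numerator and denominator do not match. The mismatch matters most in short windows. Only infected participants can have a short window, because every uninfected participant has seven days.

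As a result, two participants with identical daily symptoms can show different values on this row only because one shed virus for fewer days. The infected and uninfected columns stand side by side in Table 43, and comparing symptoms with the uninfected background is an exploratory objective (objective 7, SAP 3.1). The column for all participants in a dose group pools values that were shrunk by different factors. Dose groups that differ in infection rate or shedding length could therefore differ on this row with no difference in daily symptoms.

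**Working it through.** The SAP prints no numerical value for this variable, so there is no plan figure to reproduce. The check applies the stated rule to a known input.

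**Inputs**

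- Area: linear trapezoid over n observations, n-1 intervals (SAP 3.2.4).
- Spacing: one day, because the highest score per symptom per day is used (SAP 3.2.1).
- Divisor: n calendar days, the plain reading of SAP 3.2.5.
- Uninfected window: Days 2 to 8, so n = 7 with 6 intervals.
- Infected window: first to last positive day. The minimum is n = 2, when the only two positive days are consecutive. Positives on Days 2 and 8 alone give n = 7. Windows above 7 days arise only if positives after Day 8 are counted; SAP 5.1 lets the challenge period run to discharge, on Day 8 or later.

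**Formula**

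For a constant daily score c, the area is c(n-1). Divided by n it is c(n-1)/n. The fraction of c returned is (n-1)/n, and the uninfected reference is 6/7 = 0.857. The last column below is (n-1)/n divided by 6/7.

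| Infected window n (days) | Fraction returned, (n-1)/n | Infected relative to uninfected |
|---|---|---|
| 2 | 0.500 | 0.583 |
| 3 | 0.667 | 0.778 |
| 4 | 0.750 | 0.875 |
| 5 | 0.800 | 0.933 |
| 6 | 0.833 | 0.972 |
| 7 | 0.857 | 1.000 |
| 8 | 0.875 | 1.021 |
| 9 | 0.889 | 1.037 |

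Example: at a constant MJS of 3 per day, the 2-day window gives 3 × 0.5 = 1.5 and the uninfected window gives 3 × 6/7 = 2.57. The deficit is 1 - 1.5/2.57 = 0.42, with no difference in symptoms.

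**Scores that are not constant**

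The trapezoidal area equals the sum of the scores minus half of the first and half of the last. Area/n therefore falls below the simple mean by (c_1 + c_n)/(2n). For scores 2, 6, 2 the mean is 3.33 and area/n is 8/3 = 2.67. For 1, 3, 5, 5, 3, 2, 1 the mean is 2.86 and area/n is 19/7 = 2.71. The size of the shortfall depends on the scores at the ends of the window. For n = 2 it is always exactly half of the mean.

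**Morning and evening scores as separate time points**

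Assume assessments at 8:00 and 15:00 (the SAP says approximately 8 AM and after 3 PM). The fraction becomes (n - 1 + 7/24)/n, which is 0.646 for 2 days and 0.899 for 7 days. The direction is the same.

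**Elapsed time as divisor**

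c(n-1)/(n-1) = c, a fraction of 1.00 for every window from 2 to 9 days.

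**The case against.** The strongest reply is that the divisor is given only in words. The formula in SAP 3.2.4 weights each subarea by elapsed time, so the days summed over could mean the total of those intervals, t_n - t_1 = n-1 days. The row label fits that reading too, since an area per day is naturally an area divided by elapsed time. A programmer who took it so would produce no artefact. This stands as a possibility. It is the less natural reading, because symptoms are summed over days that carry scores and Day 2 through Day 8 is seven such days. Either way, two programmers could produce different tables from the same sentence.

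The second reply is that the stakes are low, and this is correct. Table 43 belongs to the exploratory analyses in SAP 7.2.1, whose text does not mention the area row. The table is not marked for the topline report, its shell has no p-value, and SAP 5.8 calls the analysis primarily descriptive. The same table gives the maximum cumulative MJS over fixed 5-day windows, which this issue does not touch.

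Three stronger readings may tempt a reader, and the documents do not support them.

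- **That 0.50 against 0.86 is the typical distortion.** The 0.50 needs two consecutive positive days and no others. The documents give no distribution of shedding duration, so no expected bias can be stated.
- **That infected participants are always understated.** At equal constant severity there is no relative distortion at 7 days, and beyond that it reverses slightly.
- **That half weight on the end days discards most of the information in short infections.** In a 2-day window both days count equally; in a 3-day window the weights are 0.5, 1 and 0.5. The problem is the divisor.

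**Conclusion.** The point holds on the plain wording of SAP 3.2.5. At equal, constant daily severity the infected value is 42% below the uninfected value for a 2-day window, 22% for 3 days, 12.5% for 4, 7% for 5 and 3% for 6. It is equal at 7 days and 2% to 4% higher at 8 to 9 days. The infected, uninfected and pooled entries of one row of Table 43 are affected.

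This rests on two assumptions: that the divisor is the count of calendar days in the window, and that one score per day enters the area. If the divisor is elapsed time, the artefact disappears. The SAP does not settle which is meant, so the definition needs stating under either reading.

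A reader might infer that the result of the trial is at risk. It is not. This variable does not enter the definition of symptomatic infection (SAP 3.2.1), the attack rate (Table 14), dose escalation or the choice of dose. It is a small, definite defect in a descriptive summary, worth correcting because the row should measure what its label says.

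**What to change.** In SAP 3.2.5, state that the trapezoidal area under the MJS curve is divided by elapsed time over the participant's window, t_n - t_1, and repeat this in the Table 43 row label. This keeps the planned area summary and returns a constant score unchanged for every window length.

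An acceptable alternative is the simple mean of the daily MJS over the window, which suits the present phrase about days summed and gives each day full weight. The two agree for a constant score but not in general: for scores 2, 6, 2 the area over elapsed time is 8/2 = 4.0 and the mean is 10/3 = 3.33. One of them should be named.

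The cost is one sentence in the SAP, one table label and one line of code. No new data are needed and no other endpoint changes.

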3.2.6. Mild-to-Moderate Influenza Disease (MMID-2)

In addition to the symptomatic influenza infection definition used for the primary analysis, MMID-2 will be computed based on the following criteria reported at any point during the challenge period:

1. Viral shedding detected on at least two study days by any approved positive RT-PCR assay (qualitative or quantitative, as described in [Section 3.2.2](#)) from a NP swab.
2. Any one or more of the following symptoms or signs or laboratory findings, as related to the study agent: Arthralgia, Chest tightness, Chills, Conjunctivitis, Nasal Congestion, Sinus Congestion, Coryza, Decreased Appetite, Diarrhea, Dry Cough, Dyspnea/Shortness of Breath, Fatigue/Tiredness, Fever ($>38.0^{\circ}\text{C}$), Headache, Lymphopenia (<1000 cells/mL), Myalgia, Nausea, Oxygen Saturation Decrease by $\geq 3\%$ from baseline, Productive Cough, Rhinorrhea, Sore throat, and Sweats.

Fever is determined based on temperature taken as part of vital signs assessments, and lymphopenia based on the absolute lymphocyte count assessed as part of the clinical safety labs. All other items are determined via the corresponding questions on the FLU-PRO questionnaire; component questions on FLU-PRO do not all match the language above exactly, but any reported FLU-PRO symptoms result in the threshold described in #2 being met.

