5. To compare the clinical features of symptomatic RT-PCR-positive and RT-PCR-negative illness post-challenge	a. Self- and investigator-solicited report of clinical symptoms and their severity as measured by component questions in FLU-PRO and Validation Diary and modified Jackson score by post-challenge Study Day 15 and qualitative RT-PCR positive status
6. To explore alternative case definitions (e.g., MMID or MMID-2) for symptomatic RT-PCR-positive influenza virus infection	a. The combination of symptoms and symptom severity as determined by report using the FLU-PRO and Validation Diary or modified Jackson score which optimize sensitivity and/or specificity for classifying influenza virus infection based on qualitative RT-PCR.
7. To determine the symptomatic background within uninfected participants and between sites	a. Compare symptoms from participants inoculated with shams to participants inoculated with virus

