5. GENERAL STATISTICAL CONSIDERATIONS

5.1. General Principles

The challenge period is defined as the day of study challenge (Day 1) through discharge from the confinement period (Day 8 or later).

Continuous variables will generally be summarized using the following descriptive statistics: non-missing sample size (denoted by “n”), mean or geometric mean, standard deviation, minimum, median, and maximum. Titers will be summarized with geometric means, first across replicates to compute one value for each individual sample and then across participants within clinical outcome groups. The frequencies and percentages (based on the non-missing sample size) of observed levels will be reported for categorical measures. Data listings will typically be sorted by site or other grouping variable (e.g. infection status), participant, and by visit number within participant, where appropriate. All tables will be annotated with the total population size relevant to that table, including any missing observations.

For continuous variables, confidence intervals will be computed based on the t-distribution, unless the data appear especially non-normal and the sample sizes for the analysis are insufficient to apply the central limit theorem. Bootstrap confidence intervals may be calculated instead if the t-distribution is determined to be unsuitable. For binary variables, confidence intervals will be computed using the exact Clopper-Pearson method.

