7.1.2. Influenza Symptoms

The maximum severity of influenza symptoms during the challenge period, reported as part of the Modified Jackson Score and used to determine the AR, will be summarized by challenge dose group in [Table 15](#), and separately by infection status (see [Section 3.2.3](#)) in [Table 16](#) and [Figure 7](#) (infected participants) and [Table 17](#) and [Figure 8](#) (uninfected participants). Symptoms reported on Study Day 15 will be presented similarly in [Table 18](#) and [Table 19](#). Symptoms over the challenge period will also be summarized by infection status, independent of challenge dose group, in [Table 20](#), and Day 15 symptoms will be presented in [Table 21](#).

New-onset symptoms (see [Section 3.2.3](#)) among infected participants will be summarized in [Figure 9](#), and the maximum severity of symptoms will be summarized by concurrent infection status in [Table 26](#). Wilcoxon signed rank tests will be used to compare maximum severities among infected participants: pre-infection to during infection, post-infection to during infection, and pre-infection to post-infection, in [Table 27](#). No p-value adjustment is planned for multiple comparisons, but the number of comparisons made will be considered when interpreting the results. Current/concurrent infection status is defined in [Section 3.2.3](#).

The maximum symptom severities reported for each study day during the challenge period and at any point post-challenge will be summarized for currently infected participants, separately by challenge dose group in [Table 22](#) through [Table 25](#). At baseline and Day 1, all participants will be included in these summaries, as a comparison for post-infection symptoms.

Total MJS scores during the challenge period will be presented by study day and challenge group in [Figure 10](#), with RT-PCR+ study days indicated with annotation in the given cell.

MJS symptoms will be presented in detail in [Listing 8](#).

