7.2.3. Alternative Definitions of Symptomatic Influenza Infection

While the study was not powered to establish a predictive signature of symptoms for influenza infection, exploratory analysis will be conducted to determine a predictive multi-symptom model to validate in an independent influenza challenge study.

To predict infection status, as defined by two or more days with RT-PCR+ results, the maximum severity of each symptom reported during current infection (for infected participants) or across the entire challenge period (for uninfected participants) will be included as candidate predictors in a penalized logistic regression model (lasso) [4]. The penalization parameter will be selected based on 10-fold cross-validation. The resultant model will be refit without penalization to remove the bias in estimation of the coefficients caused by the penalization parameter, with estimated odds ratios presented in [Table 46](#). The internal performance of the model in the training set will be shown in the receiver operating characteristic (ROC) curve in [Figure 15](#). The optimal cutpoint from the model, as determined by Youden's J statistic [5], will be used in a future validation of these results.

Additionally, the MMID-2 outcome will be compared with the primary symptomatic influenza infection outcome in [Table 47](#). Sensitivity analyses will also be conducted to assess varying thresholds for MJS scores and, separately, for the number of days of detectable viral shedding ([Table 14](#)).

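### SAP 3.2.6 scores MMID-2 inconsistently with its own criterion 2: the SpO2 component has no usable source, unlisted FLU-PRO items count, and the relatedness condition is not applied

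*SAP*

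**What the plan says.** SAP 3.2.6 states that "MMID-2 will be computed based on the following criteria reported at any point during the challenge period". Criterion 1 is detected shedding on two or more study days. Criterion 2 is "Any one or more of the following symptoms or signs or laboratory findings, as related to the study agent", followed by 22 named findings, among them an oxygen saturation fall of at least 3% from baseline.

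The scoring paragraph then takes fever from the vital signs and lymphopenia from the safety laboratory. For the rest, "All other items are determined via the corresponding questions on the FLU-PRO questionnaire". It concedes that the FLU-PRO wording does not match the list exactly and resolves this by saying that "any reported FLU-PRO symptoms result in the threshold described in #2 being met".

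SAP 5.1 runs the challenge period from Day 1 to discharge, on Day 8 or later. SAP 7.2.3 says that "the MMID-2 outcome will be compared with the primary symptomatic influenza infection outcome in" Table 47. This serves exploratory objective 6 (SAP 3.1), whose endpoint is the set of symptoms and severities "which optimize sensitivity and/or specificity for classifying influenza virus infection based on qualitative RT-PCR".

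**The concern.** A derived variable should compute what its definition says. Here the definition is a list of specific findings with an attribution condition. The scoring rule is any non-zero answer on a 32-item diary, and one listed finding has nowhere to come from. A programmer following the text cannot score the SpO2 component and has no rule for relatedness.

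The rule is also very easy to meet. If most infected participants meet criterion 2 through trivial or unrelated complaints, MMID-2 moves towards two RT-PCR-positive days. Table 47 would then largely set symptomatic infection against infection, which Table 14 already shows in its shedding and symptomatic-infection rows. A reader of the label could also take one slight complaint plus shedding as mild-to-moderate disease.

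**Working it through.** **Item count.** SAP 3.2.5 gives FLU-PRO 32 items scored 0 to 4. Counting the form in SAP Figure 5: 27 extent items + 3 frequency items + 2 count items = 32, which reproduces the stated number. None concerns oxygen saturation.

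**Sources for the MMID-2 list.** 22 findings less fever and lymphopenia leaves 20 assigned to FLU-PRO. Of these, 19 have a plausible FLU-PRO counterpart and one, the SpO2 fall, has none. SAP 4.6.2 has SpO2 measured about three times a day on Days 1-8, so the data exist but are not named as the source.

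**Items that count without being listed.** Dizziness, stomachache and vomiting are FLU-PRO items with no counterpart on the MMID-2 list. Under the any-symptom rule each meets criterion 2 at a score of 1.

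**Relatedness.** FLU-PRO (Protocol Appendix D) asks for extent, frequency or count over the past 24 hours. It has no attribution question, and the SAP supplies no other method.

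**Timing.** Day 1 counts towards MMID-2. For the by-day symptom tables, SAP 7.1.2 treats the same day as background: "At baseline and Day 1, all participants will be included in these summaries, as a comparison for post-infection symptoms". With a 24-hour recall, the Day 1 diary also reaches back before challenge. MMID-2 requires neither a rise over baseline nor coincidence with shedding.

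**Why some background is foreseeable.** Protocol 2.3.1 says swabs and lavage can cause watery eyes and coughing, and both are collected daily on Days 2-8. It also lists nausea (10%), vomiting (9%) and diarrhea (7%) for oseltamivir, which may start from Day 6, inside the window. All of these are FLU-PRO items.

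**Size, under assumed rates.** The documents give no FLU-PRO background rate. Let p be the daily chance of any non-zero item, with 8 diaries (Days 1-8) and independent days. The chance of meeting criterion 2 from background alone is 1 - (1 - p)^8. The last column applies (1 - p)^8 to 34 infected participants, the targeted active maximum at 10^6 TCID50 (2 × 17), as an illustration.

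| Assumed p | Meets criterion 2 | Expected of 34 not meeting it |
|---|---|---|
| 2% | 15% | 28.9 |
| 5% | 34% | 22.6 |
| 10% | 57% | 14.6 |
| 20% | 83% | 5.7 |
| 30% | 94% | 2.0 |

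If the same people report every day, the share falls towards p itself; at p = 10% the range is then 10% to 57%. Influenza symptoms in infected participants push the other way, and a stay beyond Day 8 adds diaries.

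**The case against.** Much of the case on the other side stands.

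- **The rule is permissive by design and openly stated.** Criterion 2 already asks for only one of 22 findings with no severity floor, and the FLU-PRO sentence explains a wording mismatch. Some unlisted items, such as sneezing or difficulty swallowing, sit close to listed ones. That is fair, but it does not cover dizziness, stomachache or vomiting, nor a listed finding that cannot be scored.
- **The SpO2 slip changes few classifications.** It matters only for someone with two RT-PCR-positive days, a qualifying fall, zero on all 32 items, no fever and no lymphopenia. This stands. It matters somewhat more once unlisted items stop counting.
- **Any collapse would be visible.** Table 41 shows how many infected participants had no FLU-PRO symptom, Table 42 does so for uninfected participants, and Tables 37-40 carry baseline and Day 1 columns. This stands and limits the harm.
- **The primary definition has no baseline subtraction, onset rule or relatedness judgement either (SAP 3.2.1).** Imposing the first two on MMID-2 would create a new definition, stricter in timing than its comparator. This stands, so a new-onset version belongs in a sensitivity row.

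Two stronger readings are tempting. One is that MMID-2 is simply infection under another name. The documents do not establish this. It needs a reporting rate they do not give, and treating 32 × 8 = 256 item-days as independent chances (72% at 0.5% per item-day, 92% at 1%) ignores clustering of symptoms within people, so those figures are probably too high. Eligibility also screens out recent febrile or respiratory illness, and the virologic windows differ: MMID-2 runs to discharge, while SAP 3.2.3 stops at Day 8.

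The other is that Table 47 cannot test an alternative case definition. No test is planned. Table 47 is a descriptive cross-tabulation, and objective 6 is also served by the lasso model (Table 46, Figure 15) and by the alternative score and shedding thresholds in Table 14.

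**Conclusion.** Wrong as written, in an exploratory variable. Three faults rest on the text alone: the SpO2 finding is assigned to an instrument without that item, unlisted FLU-PRO items meet a criterion that names specific findings, and the relatedness condition has no rule and no data.

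The consequence is a possibility, not a demonstrated result. Criterion 2 may discriminate little and Table 47 may add little beyond Table 14. On background alone, near-collapse appears only at assumed daily reporting of roughly 20-30% or more with independent days; at 2-5% most participants would not meet criterion 2. Influenza symptoms in infected participants would raise these shares by an amount the documents do not fix.

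A reader might carry the point over to the main results. That is not supported: MMID-2 does not enter the primary attack rate (SAP 3.2.1), the escalation rule (Protocol 9.5.6.2) or the choice of optimal dose (Protocol 9.5.2).

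**What to change.** In SAP 3.2.6:

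1. Take the SpO2 decrease from the vital-signs data, against a stated pre-challenge baseline.
2. Map each listed finding to named FLU-PRO items in a short table, and do not count items outside the map.
3. Delete the relatedness phrase or give it an operational rule.
4. Beside Table 47, add a sensitivity row that computes MMID-2 with the new-onset rule of SAP 3.2.3 (severity above baseline, from the first RT-PCR-positive day), and report FLU-PRO positivity in uninfected and sham participants. This supplements the definition and does not replace it.

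The cost is SAP wording, reprogramming of one derived variable and a few extra table rows, all from data already collected. The downside is small: somewhat fewer participants may meet MMID-2.
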